## 6. Appendix

### 6.1 Study Metrics

Metric	Justification
Patient Reported satisfaction – VAS and PPE-15	-Substantial opportunity for the Cleveland Clinic to differentiate itself among health systems and enhance revenue associated with patient satisfaction measures
Patient utilization and compliance	- Substantial opportunity for national exposure as related to national directives to drive patient engagement (See NCQA's Leadership Series: Focus on Patient Engagement at http://www.qualityprofiles.org/leadership_series/patient_engagement/index_patient_engagement.asp )
Physician and staff satisfaction	- Opportunity to demonstrate clinical adoption rates and low barriers to implementation.
Total 90 day post-operative cost from index date+1 (same day) or from index date + LOS (inpatient)*  *Claims submitted within 90 days must be limited to ICD-10 listed below (or if hospitalization due to ICD-10 below) in order to exclude unrelated claims.	Joint Coach templates should be able to either prevent the complication, or through early detection at the clinic level, reduce expense through minimized emergency room visits and readmissions.
30 day post-op hospitalization rate (this is a readmission if initially an inpatient procedure, or an admission if initially an outpatient procedure)*  *Must be associated with ICD-10s listed below in order to exclude unrelated readmissions.	
30-day ED Visit Rate*  *Must be associated with ICD-10s listed below in order to exclude unrelated ED visits.	
Number of follow up visits within 90 days	Demonstration to physicians and practices the potential to improve throughput and workflow efficiency by minimizing the number of follow up visits required.
Potentially preventable readmissions and complications identified using JointCOACH	Potentially preventable admissions, events, ED visits. Using an approach similar to 3M's Potentially Preventable Events grouping software, we will examine all events (ED visits, admissions, complications) for relation to index event, and compare this rate to prior year. Data may be supplemented by Physician survey. http://solutions.3m.com/wps/portal/3M/en_US/Health-Information-Systems/HIS/Products-and-Services/Products-List-A-Z/PPR-and-PPC-Grouping-Software/

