## **2. Introduction and Background**

Health systems invest significant resources to improve quality and reduce costs. However, this process is typically driven by hospital administration and staff. Recently, studies have shown that when patients are engaged, they take more responsibility for their own health and preventative care. Additionally, these patients are more satisfied with their healthcare experiences and have lower rates of healthcare utilization . Physicians are in the best position to promote patient engagement since they have direct relationships with their own patients. However, physicians need frictionless tools with minimal implementation barriers in order to create and maintain this relationship in the follow up period.

Patient engagement has been referred to as the next blockbuster “drug”, and increasing evidence demonstrates that highly engaged patients not only enjoy improved outcomes, but have fewer complications, undergo fewer readmissions, and have lower total costs of care . While these engagement-related outcomes have been shown in several other specialties, relatively little has been done to explore this relationship in orthopedics. The opportunity to demonstrate the

impact of engagement on outcomes in the orthopedic space is highlighted by the estimated \$1.5B of medical expenses occurring nationally due to potentially preventable readmissions following orthopedic surgeries alone.

Stryker Performance Solutions JointCOACH™ and the Cleveland Clinic are interested in collaborating on a clinical pilot study to demonstrate that high patient engagement leads to enhanced preoperative preparation potentially reducing length of stay (LOS), readmissions and reoperations, increasing discharge disposition to home rather than another facility, reducing the need for in-person follow up, and increasing patient (and provider) satisfaction after elective primary hip and knee arthroplasty (THA and TKA). These improvements can translate to higher financial savings through the episode of care especially in light of the alternative payment models.

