### **3. Specific Aims**

Currently in use by orthopedic groups around the country, JointCOACH improves perioperative outcomes after THA and TKA and mitigates risk by: 1) enhancing patient engagement with providers, 2) allowing patients to play an integral role in patient-reported outcomes, 3) generating and relaying actionable pre- and postoperative reporting directly to the clinical team, and 4) detecting impending postoperative complications early, enabling timely intervention and preventing avoidable complications and readmissions. The specific aims of this proposal are to:

1. Measure patient satisfaction with and without use of JointCOACH as a tool for patient engagement
2. Understand the degree to which high postoperative engagement can reduce the amount of healthcare resource utilization by answering the following questions:

- a. Will the use of JointCOACH decrease the number of potentially avoidable healthcare utilization encounters such as Emergency Department (ED) and hospital visits (i.e. readmissions and reoperations)?
  - b. Does utilizing JointCOACH improve clinical workflow by minimizing telephone calls and thereby offloading support staff, allowing them to be more efficient?
  - c. Does utilizing JointCOACH reduce the volume of on-call pages by addressing patient questions up front, alleviating concerns, and providing them with the information they need when they need it?
  - d. Does utilizing JointCOACH allow the practice to identify patients whose in-person follow-up needs are minimal?
3. Measure additional potential benefits including shorter length of hospital stay, discharge disposition to home rather than a facility and decreased 90 day readmissions and reoperations by answering the following:
  - a. Does utilizing JointCOACH lead to early detection of adverse signs/symptoms that develop between clinical encounters and result in reduced readmissions and reoperations?
4. Evaluate the financial impact of JointCOACH in the episode of care (% difference in Charges between JointCOACH and standard of care groups)

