## 6.2 ICD-10 codes for relevant metrics

Description	ICD-10

 
1. Must be in 1st or 2nd diagnosis and must not be chronic, or
 
	

 
2. If patient is admitted, must be in 1st or 2nd diagnosis on hospital discharge.
 
	
Infection and inflammatory reaction due to internal prosthetic device, implant, and graft 
 
• Due to unspecified implant, device, and graft
 
• Due to internal joint prosthesis
 
• Due to other internal orthopedic device, implant and graft
 
	T8579XA T8450XA T8460XA
Other complications of internal prosthetic device, implant, and graft 
 
• Due to unspecified implant, device, and graft
 
• Due to internal joint prosthesis
 
• Due to other internal orthopedic device, implant, and graft
 
	T859XXA T8481XA- T8486XA; T8489XA; T849XXA
Postoperative infection 
 
• Other post-operative infection (abscess, septicemia)
 
	K6811 T814XXA
Disruption of wound 
 
• Dehiscence of operation wound
 
	T8130XA- T8132XA
Infections of Skin and Subcutaneous Tissue 
 
• Upper arm and forearm
 
• Leg except foot
 
• Abscess NOS, Cellulitis NOS
 
	LO3119 LO3129 LO390 LO391
Gastrointestinal hemorrhage 
 
• Hematemesis
 
• Melena
 
• Hemorrhage of gastrointestinal tract, unspecified
 
	K920 K921 K922
Hemorrhage NOS	R58
Venous embolism and thrombosis of deep vessels of lower extremity 
 
• Of unspecified site
 
	I82409 I8291
Pulmonary embolism and infarction	I2690 I2692 I2699 T82817A, T82818A
Since ED coding is often not as precise as the above, we will likely need to also have these below	
Fever unspecified	R502 R509 R5081- R5094 R6883
Systemic inflammatory response syndrome due to infectious process without acute organ dysfunction	A419
Severe sepsis	R6520
Joint Replacement DRGs	461-462, 469-470
Hip and Knee specific DRGs	466-468, 488-489

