### 6.3 Success Thresholds for Study Metrics

Metric	Threshold	Rationale
Patient reported (0) satisfaction	$\geq 70\%$ satisfied or very satisfied	Value is consistent with most of the Medicare value based purchasing programs. 70% also exceeds thresholds targeted by several other large health systems.
Patient engagement	$\geq 70\%$ of members are $\geq 60\%$ engaged with the Joint Coach software	
Physician satisfaction	$> 80\%$ physician satisfaction	
Total 90 day post-operative cost (claims submitted) from index date+1 (same day) or from index date + LOS (inpatient)	No increase in cost during pilot study relative to cost averaged across 3 prior years (costs to be adjusted for inflation using either the medical care component of the Bureau of Labor Statistics Consumer Price Index, or The health system internal inflation index if available.)	Standard inflationary cost adjustment in medical economics is the medical care component of the CPI, or using a 3% discount rate.
30-day post-op hospitalization rate	$< 4\%$ considering the UHC national average	
30-day ED visit rate		
Number of follow up visits within 90 days		
Potentially preventable admissions		

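### The only defined cost measure omits the index stay and most uncoded care, so it does not give the episode charges Aim 4 asks for, and its inpatient window moves with length of stay

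*Combined protocol and SAP*

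**What the plan says.** Section 3, Aim 4, is to "Evaluate the financial impact of JointCOACH in the episode of care", expressed as the percentage difference in charges between the two groups. Section 1 describes the episode as running from the scheduling of surgery to at least 90 days after it. Section 2 describes the platform as "potentially reducing length of stay (LOS), readmissions and reoperations, increasing discharge disposition to home rather than another facility", along with less in-person follow-up, and says these gains can become savings over the episode. Aim 3 makes length of stay (LOS) and discharge disposition outcomes.

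One cost measure is defined. Appendix 6.1 gives it as "Total 90 day post-operative cost from index date+1 (same day) or from index date + LOS (inpatient", and its footnote adds: "Claims submitted within 90 days must be limited to ICD-10 listed below", or to hospitalisations due to those codes. Its justification is to prevent complications or, through early detection, to "reduce expense through minimized emergency room visits and readmissions". Appendix 6.3 repeats the window ("Total 90 day post-operative cost (claims submitted) from index date+1 (same day) or from index date + LOS (inpatient"), does not restate the code limit, and sets the success threshold against the average of three prior years.

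The outcome list in 4.1 and the Schedule of Events in 4.4 have no cost item, and 4.5 has no cost analysis.

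**The concern.** The aim is an episode-of-care comparison, but the only definition a data analyst could apply is a post-discharge, complication-related cost. If it is used for Aim 4, for want of anything else, two things follow.

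First, some of the expected savings cannot appear in it. Days of inpatient stay saved fall outside the window, and facility care or follow-up visits avoided fall outside the code limit unless the claim carries a listed code.

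Second, for inpatients the window opens at discharge, and discharge timing is something the intervention is meant to change. A complication on postoperative day 3 is counted for a patient who went home on day 2, but is absorbed into the index stay for a patient still in hospital. The two randomised arms could therefore be observed over different postoperative days.

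At stake is whether the financial result answers Aim 4, and whether a shorter stay could make the intervention arm look more expensive than it was.

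**Working it through.** The plan gives no sample size, standard deviation or effect size for cost, so there is no cost figure to reproduce. The 153 per group in 4.3 concerns the PPE-15 and does not enter here.

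**Step 1. Expected savings set against what 6.1 counts**

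| Component | Named as an expected benefit | Inside the 6.1 window | Counted |
|---|---|---|---|
| Index inpatient days | Section 2, Aim 3 | No | No |
| Facility care after discharge | Section 2, Aim 3 (home discharge) | Yes | Only with a listed code |
| Follow-up visits | Section 2, 6.1 | Yes | Only with a listed code |
| ED visit or readmission for a listed complication | Section 2, Aims 2 and 3, 6.1 | Yes | Yes |

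6.2 also requires the listed code to be in first or second diagnosis position.

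If stay falls by d days at a daily charge c, episode charges fall by c × d. The 6.1 measure changes by 0 for any c and d, because those days precede its start. This step needs no assumed values.

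**Step 2. How the window moves**

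In days after the index date, the start is day 1 for same-day cases and day LOS for inpatients. The text does not say whether the 90 days run from this start or from surgery, so both are shown.

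| LOS | Start | End, if 90 days run from start | Length, if 90 days run from surgery |
|---|---|---|---|
| Same day or 1 | 1 | 91 | 89 |
| 2 | 2 | 92 | 88 |
| 3 | 3 | 93 | 87 |

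From LOS 1 upward, each further inpatient day moves the start by one day. Same-day cases have a fixed start, the same as LOS 1.

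**Step 3. Size of the shift**

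Assumptions, none of them in the documents: identical complication cost by day since surgery in both arms, no treatment effect, every patient in one arm at LOS a and every patient in the other at LOS b. Cost is either even over time or declines exponentially with mean m days. The share counted between start s and end e is:

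- even: (e − s)/90
- declining: [exp(−s/m) − exp(−e/m)] / [1 − exp(−90/m)]

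Excess in the shorter-stay arm = share(a)/share(b) − 1.

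Examples: even cost, 90 days from surgery, LOS 1 vs 2: (89/90)/(88/90) − 1 = 1.1%. Mean 7 days, LOS 1 vs 2: 0.8669/0.7515 − 1 = 15.4%.

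| Cost timing (assumed) | LOS 1 vs 2 | LOS 1 vs 3 |
|---|---|---|
| Even over 90 days | 0% to 1.1% | 0% to 2.3% |
| Mean 30 days | 3.4% to 3.6% | 6.9% to 7.3% |
| Mean 14 days | 7.4% | 15.4% |
| Mean 7 days | 15.4% | 33.1% |

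Ranges within a cell cover the two readings of the 90 days. The direction is the same throughout: the shorter-stay arm is never favoured.

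**The case against.** The best defence is that 6.1 and Aim 4 are different quantities. Aim 4 speaks of charges over the episode. The 6.1 row speaks of post-operative cost, has its own complication-based justification, and uses its code limit deliberately to exclude unrelated claims. For that purpose it is a reasonable measure. LOS, disposition and follow-up visits are also collected separately, though not in money. This stands in part. The documents never call the 6.1 row the Aim 4 measure, so a reader who inferred that the trial cannot detect savings from shorter stay would go too far: Aim 4 as worded could include the index stay. What remains is that nothing else in the plan defines Aim 4.

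Four narrower objections also limit the point:

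- **Facility care.** It falls inside the window; the code limit removes it, not the start date. The exclusion of planned skilled nursing facility discharges in 4.2 shrinks this route but does not close it, since unplanned and other facility discharges remain.
- **Code list.** It would be loose to say that only complication codes count. 6.2 also lists fever and sepsis codes for imprecise ED coding, and rows such as "Joint Replacement DRGs" with no stated use. If those rows selected claims, and claims were dated by submission, the index claim might enter. The footnote's limit to ICD-10 and the start at discharge make exclusion the natural reading.
- **Extra day of observation.** A shorter stay lengthens the window only if the 90 days run from surgery. If they run from discharge, the window keeps its length and shifts.
- **Data.** The documents do not show that outside facility charges are available, and removing every diagnosis limit is partly a trade-off, not a correction.

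**Conclusion.** The point holds as a mismatch between a stated aim and the only measure defined for cost. Followed as written, the 6.1 measure gives no credit for inpatient days saved, whatever a day costs. It credits facility care and follow-up visits avoided only where a listed code is present. These conclusions follow from the definition, on the natural reading of 6.1 and 6.2.

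The dependence of the inpatient window on LOS is also real, and it works against the shorter-stay arm. Its size is not established. It is negligible to small if costs are spread evenly (at most 2.3% for LOS 1 vs 3) and larger if they fall early (15% for LOS 1 vs 2 and 33% for LOS 1 vs 3 with an assumed 7-day mean). Both the stays and the cost timing are assumed.

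A reader might infer that the measure is likely to turn a true saving into a reported increase and so fail the no-increase threshold in 6.3. That is possible, but the documents give nothing to show it is likely. The historical comparator in that threshold is a separate matter; changing it alone would leave the window and scope as they are.

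Cost is not the primary endpoint, so the PPE-15 analysis and its sample size are untouched. The definition should still be settled before charges are extracted.

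**What to change.** In 6.1 and 6.3, define the Aim 4 measure as charges per patient from the date of surgery, index stay included, through a fixed postoperative day 90, compared between the randomised arms. Include post-acute and follow-up charges where the health system's records hold them, and say which sources those are.

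Keep the figure limited to the 6.2 codes as a secondary measure, labelled complication-related post-discharge cost. End it at day 90 from surgery in both arms, and state that its start depends on LOS for inpatients.

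The cost is a wording change in the appendix and a broader pull of charges. Episode charges will be more variable than code-limited ones, by an amount the documents do not allow to be estimated; that is one reason to keep the coded figure alongside. Enrolment and the primary analysis do not change.

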## **4. Methods**

### **4.1 Study Design**

The study design is a prospective, randomized trial in which patients undergoing elective primary hip or knee arthroplasty will be offered perioperative use of JointCOACH vs standard of care. A total of 400 patients will be enrolled (200 in each group). The following outcome measures will be collected at the intervals specified in the Schedule of Events:

- Demographics (Age, gender, BMI)
- Comorbidities (Age-Adjusted Charlson Comorbidity Index)
- Surgical details (ASA (or other comorbidity index), Length of surgery (incision to closure), procedure type, operative limb, surgeon)
- Length of hospital stay and discharge disposition
- Number of ED visits and follow-up visits within 90 days
- Number of phone calls and on-call pages within 90 days
- Readmissions and reoperations within 90 days
- Patient satisfaction (VAS satisfaction and PPE-15)
- Provider satisfaction (5-point Likert scale)

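### The preventable-events metric in Section 6.1 is labelled by a tool only one arm has, conflicts with its own method, and has no arm-neutral ascertainment or masking

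*Combined protocol and SAP*

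**What the plan says.** The last row of the table in Section 6.1 names the metric "Potentially preventable readmissions and complications identified using JointCOACH". The cell beside it gives the method. It describes the classification as "Using an approach similar to 3M's Potentially Preventable Events grouping software". Of the events and their comparator it says "we will examine all events (ED visits, admissions, complications) for relation to index event, and compare this rate to prior year". It adds: "Data may be supplemented by Physician survey".

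Section 4.1 describes a randomised trial in which patients "will be offered perioperative use of JointCOACH vs standard of care". Section 3 says the tool works by "generating and relaying actionable pre- and postoperative reporting directly to the clinical team" and by "detecting impending postoperative complications early, enabling timely intervention and preventing avoidable complications and readmissions".

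The rows for 90-day cost, 30-day hospitalization and 30-day ED visits in Section 6.1 each carry a footnote restricting them to the ICD-10 codes listed in Section 6.2. The preventable-events row has no such footnote and gives no time window. Section 6.3 lists potentially preventable admissions without a threshold. Section 4.5 gives an analysis for the PPE-15 only. The documents do not say who classifies events, by what criteria, or whether that person is masked to arm.

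**The concern.** The label ties the event count to the intervention's own reporting channel. An event in a standard-of-care patient cannot be found with a tool that the patient does not have. The method cell points to a wider set of events, so two analysts could follow the same row and count different things.

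The wider reading does not remove the problem. Admissions and ED visits leave a record in either arm. Complications are also counted, and a mild one may become known only because a JointCOACH patient answered a survey. Whether an event is related to the index operation is then a judgement, with no stated criteria and no stated masking, and a survey of physicians may add to it.

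Extra detection would raise the count in JointCOACH patients. Lenient classification by someone who knows the arm could lower it. A reader could not tell which had happened, so neither an apparent benefit nor an apparent lack of one could be taken at face value. The metric bears on the utilization question in Aim 2a and the early-detection question in Aim 3a.

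**Working it through.** **Label against method (Section 6.1, same row)**

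1. *Which events.* The label covers readmissions and complications found through the tool. The method covers all ED visits, admissions and complications. ED visits appear only in the method, and the restriction to the tool appears only in the label.
2. *Which comparison.* Section 4.1 randomises patients to JointCOACH or standard of care, and Aims 2 and 3 ask what the tool changes. The row compares with the prior year instead. The documents do not say whether prior-year patients used the tool. If they did not, the same asymmetry of detection applies and the protection of randomisation is lost as well.
3. *How events are found.* Section 1 says surveys sent through JointCOACH keep the surgical team informed. No equivalent channel is described for standard of care.
4. *How events are classified.* The approach is only similar to a named software, the code list is not invoked, and no masking is stated.

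**Size**

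The documents give no rate for this metric, so there is no figure of the plan's to reproduce here. The only computed figure in the plan belongs to the PPE-15: 2 × (1.96 + 0.842)² × 7.7² / 2.47² = 152.6, rounded up to 153 per group, with 2.47 taken as 10% of 24.7. This point does not alter it.

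To show what unequal capture could do, I assume:
- 200 patients per group (Section 4.1);
- the same true event rate *p* in both groups, assumed 4%, 8% or 15%;
- full capture in JointCOACH patients, and capture of a fraction *r* in the comparator, assumed 90%, 75% or 50%;
- a two-sided 5% test of two proportions, normal approximation.

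The comparator's observed rate is *rp*, the apparent rate ratio is 1/*r*, and the spurious difference is *d* = *p*(1 − *r*). With the mean rate *m* = *p*(1 + *r*)/2, SE₀ = √[2*m*(1 − *m*)/200] and SE₁ = √{[*p*(1 − *p*) + *rp*(1 − *rp*)]/200}. The chance of a false difference is 1 − Φ[(1.96·SE₀ − *d*)/SE₁] + Φ[(−1.96·SE₀ − *d*)/SE₁].

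Worked case, *p* = 4%, *r* = 50%: *d* = 0.02, SE₀ = 0.01706, SE₁ = 0.01703. The two terms are 1 − Φ(0.789) = 0.215 and Φ(−3.14) = 0.001, together 21.6%.

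| True rate | Capture | Expected events, JointCOACH vs comparator | Apparent ratio | Chance of false difference |
|---|---|---|---|---|
| 4% | 90% | 8 vs 7.2 | 1.11 | 5.5% |
| 4% | 75% | 8 vs 6 | 1.33 | 8.4% |
| 4% | 50% | 8 vs 4 | 2.0 | 21.6% |
| 8% | 90% | 16 vs 14.4 | 1.11 | 6.0% |
| 8% | 75% | 16 vs 12 | 1.33 | 12.3% |
| 8% | 50% | 16 vs 8 | 2.0 | 39.1% |
| 15% | 90% | 30 vs 27 | 1.11 | 7.1% |
| 15% | 75% | 30 vs 22.5 | 1.33 | 19.9% |
| 15% | 50% | 30 vs 15 | 2.0 | 66.2% |

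Here the error runs against JointCOACH. If unmasked classification removed the same fraction of events from JointCOACH patients instead, the formula is symmetric and the same probabilities would apply in the tool's favour.

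**The case against.** The strongest reply is that the row's own method says "we will examine all events (ED visits, admissions, complications) for relation to index event". On that reading control events are counted, and the label is merely loose. A reader might infer from the label that no control event could ever count, but the row does not settle this. What stands is a conflict between label and method, which leaves the counting rule open.

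Second, a reader might infer that the people judging events know the arm. The documents do not say so. They name no reviewer and do not say that reviewers see JointCOACH messages; an approach modelled on grouping software could be largely mechanical; and the survey is optional and of unspecified physicians. What stands is that nothing prevents unmasked review, and that an event arriving through the tool discloses the arm.

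Third, the row's comparison is historical, so a bias between arms is not what it would produce as written. That is correct, but the asymmetry of detection may carry over to the prior-year comparison.

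Fourth, Aim 3a does not depend on this row. Section 4.1 lists 90-day readmissions and reoperations as separate outcomes, not limited to events found through the tool, and Section 4.4 schedules their tracking. This limits the consequence and stands in full. Section 6.2 is also titled broadly enough that its codes may have been meant for this row; the row does not say so.

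**Conclusion.** The concern holds as an ambiguity with a risk of bias. The label cannot be applied to standard-of-care patients, the method and comparator beside it say something else, and neither ascertainment nor classification is protected. Rates may differ between JointCOACH patients and any comparator for reasons other than a true effect, in either direction. The documents do not support saying that they will differ.

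The size cannot be computed from the documents. The ranges above rest wholly on assumed rates and capture fractions: at 90% capture the effect on the test is slight (5.5% to 7.1% against a nominal 5%), and at 50% it is serious (21.6% to 66.2%). A reader might take the threshold of below 4% in Section 6.3 as this metric's rate. It belongs to 30-day hospitalization, a narrower endpoint restricted by code, and cannot serve for a mix of ED visits, admissions and complications.

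This is a secondary appendix metric with no stated threshold and no planned test. The PPE-15 primary endpoint and its sample size are unaffected.

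**What to change.** In Section 6.1, with matching wording in 6.3:

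- Rename the metric: potentially preventable ED visits, admissions and complications, by randomised arm.
- Count events in both arms from the same source (medical record or claims), with one stated window and the Section 6.2 code list.
- Make the randomised comparison the comparison for this metric, and keep the prior year as description only.
- List events known only through JointCOACH separately, as a descriptive measure of the JointCOACH arm.
- Do not use the physician survey as a source of events.
- State who classifies events, and have them work from summaries with the arm and any JointCOACH messages removed.

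Do not add a new patient question for controls to equalise detection. That is extra data collection, and it could give controls part of the intervention.

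The cost is a few lines of appendix wording and the work of redacting case summaries. A few mild complications seen only in JointCOACH will leave the count, and masking may be imperfect.
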